- interventions and Buration
 - Explanation of the study and confirmation of eligibility
 - Measurement of height, weight, waist and hip circumference, blood pressure
 - and pulse
 - Review of medical history
 - o Blood tests
 - Questionnaires about general health and well-being, COVID-19 questionnaire quality of life, sleep, emotional health and mood and pregnancy history.
 - Neurocognitive tests
 - Brain magnetic resonance imaging (MRI)
 - Brain positron emission tomography (PET): F-18 Florbetapir PET (all sites) and F-18 AV-1451 PET (only at the Mayo Clinic & BAI site)
 - All tests and procedures will take about 9 hours total to complete.

Participants will be on study until all of the following are completed: medical assessment, questionnaires, blood work, neurocognitive studies, , brain MRI, brain PET.

Sample Size and Population

Our targeted enrollment is 492 (n=83 at the Mayo Clinic) participants across eight sites; 13 years post-randomization (4 years of study drug and 9 years after the end of study drugs).

Women who enrolled in the KEEPS study at 8 sites will be invited to participate (total n=688; Mayo Clinic n=118). In order to reduce the costs but retain as many participants as possible, we merged the cohorts in two sites by taking advantage of the proximity of geographic location. Columbia University will be recruiting the Einstein Montefiore Center's participants; therefore 7 sites including Mayo Clinic Rochester will be participating.

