At Mayo Clinic, 118 women met the inclusion criteria for randomization into the KEEPS trial. This study will recruit these 118 menopausal women for follow-up. Assuming a 70% retention rate, we project that our cohort will consist of approximately 82 subjects.

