8. STATISTICAL CONSIDERATIONS

9.1 General Design Issues

The proposed analytical plan will comprise 1) data cleaning and basic statistical analyses to identify potential outliers, assess for normality, and examine variation in each variable; 2) the generation of standard descriptive statistics summarizing the sample and its characteristics; and 3) statistical methods for analyzing each specific aim and hypothesis. For each aim, all calculated P values will be 2-sided and P<.05 will be considered statistically significant.

9.2 Primary Objective 1

To determine the differences in A β , cerebrovascular lesion load and brain structure in postmenopausal women who were treated with one of two mHTs vs. placebo after 13 years post-randomization and 9 years after the end of mHT administration phase.

Primary Hypothesis: Aβ PET SUVR (primary outcome), AV-1451 SUVR, WMH volume and regional cortical thickness (or hippocampal volume) are different in women who were treated with tE2 vs. placebo and oCEE vs. placebo.

Hypothesis 1a: Aβ PET SUVR (primary outcome), AV-1451 SUVR, WMH volume and regional cortical thickness (or hippocampal volume) differences in women who were treated with tE2 vs. placebo and oCEE vs. placebo are modified by the *APOE*e4 status (carrier/noncarrier).

Hypothesis 1b: Aβ PET SUVR (primary outcome), AV-1451 SUVR, WMH volume and regional cortical thickness (or hippocampal volume) differences in women who were treated with tE2 vs. placebo and oCEE vs. placebo during early post menopause are modified by the vascular disease risk at 13 years post-randomization.

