Statistical Analysis for Aim 1: We will first summarize the data for Aim 1 using standard descriptive statistics and a variety of plots (histograms, scatterplots) to assess variable distributions. Our outcome measures: Aß PET SUVR (primary outcome), WMH volume, and regional cortical thickness (or hippocampal volume) for this aim will all be continuous crosssectional variables, we will use analysis of covariance (ANCOVA) to address the primary hypothesis. Treatment groups (tE2, oCEE, and placebo) will be included as the predictors of interest, coded so that placebo is the reference group. Standard methods (Least Significant Difference, Tukey's Honest Significant Difference, and Scheffé's test) will be used to assess pairwise differences. We will include a set of dummy variables to test and adjust for site (block) effects. The outcome variables will be transformed as necessary to meet regression assumptions underlying the ANCOVAs. These analyses will include baseline age, time from baseline, and APOE ε4 status (as appropriate) as covariates. We will test for interactions of treatment with APOE ε4 status through inclusion of two-way interactions in the models, and analyses in separate APOE £4 non-carrier and APOE £4 carrier strata. To address Hypothesis 1a, we will expand the set of covariates to include a vascular disease risk score assessed at the time of mHT/placebo initiation(82) or individual cardiovascular risk factors (systolic and diastolic BP, fasting glucose, smoking history, lipid profile, BMI, waist circumference). Possible interactions with these covariates will be handled in the same way as APOE ε4 status. Hypothesis 1b will be treated much the same way, but CVD risk scores will be constructed from data acquired at 13 years after initiation of mHT. Since some of the women in the study might have used mHT after the trial ended, we will perform a series of sensitivity analyses with and without those individuals to assess any important effects and ensure that the final conclusions are robust.

Power for Aim 1: Focusing on Florbetapir PET, our primary outcome variable for Aim 1, we first estimated the standard deviations in three groups of women (all subjects, APOE ε4 non-carriers, and APOE ε4 carriers) from the Mayo Clinic Study of Aging, a longitudinal study on aging and dementia. We identified women with an age range of 55-70 (mean age=65) similar to our projected sample, who underwent both Aβ PET imaging and APOE ε4 testing (n=264) Using

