Power for Objective 2: Power and sample size estimates to detect significant changes in cognitive function are based on Mayo Clinic pilot data collected over five unequally-spaced observation time points (0,18, 36, 48, and 84 months) with the verbal learning and memory factor as the longitudinal outcome and treatment groups vs. placebo as predictors. We assumed normally distributed continuous outcomes with missing data, two predictors (oCEE and tE2) with regression coefficients in factor score units for rate of change of, respectively, -0.20 and -0.11; a variance of 2.09 for the random intercept, a variance of 0.03 for the random slope, and a correlation between random slope and random intercept terms set to 0.07. Using a two-tailed α =0.05, a total sample size of 492 individuals will achieve a power of 82% to reject the hypothesis for this aim.

Alternative Strategy: We will evaluate our participants for incident MCI and dementia, but we do not expect to have sufficient power to test the differential progression to MCI or dementia in each of the mHT vs. placebo groups. However, we will explore this alternative approach if we have a sufficient number of incident cases.

9.4 Primary Objective 3

To determine the associations between imaging biomarkers investigated in Aim 1, and longitudinal changes in cognitive performance and mood investigated in Aim 2.

Primary Hypothesis 3: Higher Aβ (primary outcome), AV-1451 and WMH load, and smaller regional cortical thickness are associated with a longitudinal decline in cognitive performance since randomization

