Statistical Analysis for Objective 3: Repeated cognition and mood measures will be available for time points ranging from trial baseline to 13 years post-baseline; we will use the same cognitive factor scores and POMS as in Aim 2. For each measure in Aim 2, we will consider the values at year 13, the changes in values from baseline to year 13, and predicted annual changes in values at year 13 (slopes). Aβ PET SUVR, WMH, and AD signature thickness and hippocampal volume will only be available at 13 years post-baseline. We will use plots and Pearson or Spearman correlation coefficients, as appropriate given the distributions of the variables involved, to describe and measure associations between cognitive/mood measures and imaging biomarkers. As in the previous aims, we will explore and include site and covariate effects through regression models, transform variables as needed to meet assumptions, and perform sensitivity analyses with and without individuals who continued to use mHT after the mHT administration phase ended.

Power for Objective 3: With 492 individuals and α =0.05, we will have 80% power to detect Pearson correlation coefficients as small as 0.127. In a linear regression, this would be an increase in the model R² due to the association of interest as small as 0.016. We should thus have sufficient power to detect small associations.

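### The Objective 3 power statement assumes 492 women, but tau PET, named in Primary Hypothesis 3, is planned for about 129, where power at r = 0.127 is about 30%

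*Combined protocol and SAP*

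**What the plan says.** Section 9.4 has a single power statement for Objective 3. Using all 492 women and α = 0.05, it says "we will have 80% power to detect Pearson correlation coefficients as small as 0.127", equates this with an R² increase of 0.016, and ends: "We should thus have sufficient power to detect small associations". It is not limited to any marker.

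Primary Hypothesis 3, in the same section, goes beyond amyloid. After Aβ (marked as the primary outcome) it continues: "AV-1451 and WMH load, and smaller regional cortical thickness are associated with a longitudinal decline in cognitive performance". The Primary Hypothesis in section 9.2 also includes tau: "AV-1451 SUVR, WMH volume and regional cortical thickness (or hippocampal volume) are different in women who were treated with tE2 vs. placebo".

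The Précis (Interventions and Duration) gives florbetapir PET at all sites but "F-18 AV-1451 PET (only at the Mayo Clinic & BAI site". Table 1 in section 4, which already assumes 70% participation, projects 83 women at Mayo and 46 at Banner Alzheimer's Institute. The text of section 4 puts Mayo one lower: "Assuming a 70% retention rate, we project that our cohort will consist of approximately 82 subjects".

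Neither analysis paragraph lists tau. The Aim 1 outcome list names Aβ PET SUVR and then "WMH volume, and regional cortical thickness (or hippocampal volume) for this aim will all be continuous crosssectional variables". The Objective 3 list names Aβ PET SUVR and then "WMH, and AD signature thickness and hippocampal volume will only be available at 13 years post-baseline".

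**The concern.** A power statement made for a whole objective should hold for each marker its primary hypothesis names, or say where it does not. Here one of the named markers will be measured in about a quarter of the women (129/492 = 26%), and no tau-specific N, detectable size or analysis text is given.

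What is at stake is how a null tau result would be read. Anyone relying on section 9.4 could take it as evidence against a small tau–cognition association, when the study would have had little chance of finding one. Aim 1 carries a similar risk. Its power paragraph concludes that power is adequate for florbetapir and then adds that effect sizes for the remaining outcomes should be similar. For tau, a similar effect size would not bring similar power.

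**Working it through.** **Inputs**
- N = 492, r = 0.127, 80% power: section 9.4.
- Two-sided α = 0.05: section 9.1.
- Tau PET at Mayo and BAI only: Précis.
- Mayo 83 and Banner 46: Table 1. Sum 83 + 46 = 129, or 82 + 46 = 128 with the section 4 text.
- All 118 Mayo women from the original trial: section 4.
- Full participation at Banner is not given. Assumed 46/0.70 ≈ 66, so the two-site maximum is about 118 + 66 = 184.

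**Formulas (Fisher z)**
- Power = Φ(atanh(r)·√(n−3) − 1.960) + Φ(−atanh(r)·√(n−3) − 1.960)
- Detectable r at 80% power = tanh((1.960 + 0.842)/√(n−3))

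**The plan's own figure.** atanh(0.127) = 0.1277 and √489 = 22.11, so the product is 2.824. Power = Φ(2.824 − 1.960) = Φ(0.864) = 80.6%. Detectable r is 0.126, and 0.127² = 0.016. The printed figures reproduce.

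**The tau subsample.** √126 = 11.22, so the product is 1.433. Power = Φ(1.433 − 1.960) = Φ(−0.527), which with the negligible opposite tail gives 30.0%. Detectable r = tanh(2.802/11.22) = 0.245. A t-based version, a noncentral F version and a simulation give 30.1%, 30.3% and 29.8%.

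| Women with tau PET | Power at r = 0.127 | Detectable r (80%) | R² |
|---|---|---|---|
| 492 (as stated) | 80.6% | 0.126 | 0.016 |
| 184 (full participation, assumed) | 40% | 0.205 | 0.042 |
| 129 (Table 1) | 30.0% | 0.245 | 0.060 |
| 128 (Mayo 82) | 29.8% | 0.246 | 0.060 |
| 100 to 120 (assumed incomplete scanning) | 24% to 28% | 0.277 to 0.253 | 0.077 to 0.064 |

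Solving for n at r = 0.127 and 80% power: (2.802/0.1277)² + 3 = 484.4, or about 485 women.

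**Aim 1, tau (two-sample t, equal arms assumed).** As a check, 492/3 = 164 per arm gives a detectable d of 0.310, in line with the 0.308 and 0.312 in Table 3. With 129/3 = 43 per arm, detectable d is 0.61, and power at the pilot d = 0.34 is 34%. With 184/3 ≈ 61 per arm, the figures are 0.51 and 46%.

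**APOE ε4 strata, tau.** These figures are conditional. They assume that 25% are carriers (the share Table 3 implies) and that the pilot effect sizes apply to tau; the documents do not say which outcome gave them. Power is then 31% in non-carriers at d = 0.37 and 74% in carriers at d = 1.18 (63% to 82% for 20% to 30% carriers). The conclusion does not depend on them.

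**The case against.** The best defence is that the 492-based sentence was never meant for tau. The analysis paragraph just before it lists only markers collected at all sites, the Aim 1 outcome list also leaves out AV-1451, and Aβ is marked as the primary outcome throughout. Power is normally stated for the primary outcome, and the arithmetic for 492 women is right.

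Part of this stands. It is a fault of scope, not a miscalculation, and Aβ is unaffected. But the power statement is made for the objective as a whole, the hypothesis it serves names AV-1451, and its closing sentence generalises without exception. The missing tau entry in the analysis lists is a second gap and does not serve as a restriction.

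Three further points are fair:
- r = 0.127 is the smallest correlation detectable with 492 women, not an expected tau effect. The 30% is therefore conditional on that value, and the detectable r is the more useful number.
- The Aim 1 remark concerns effect sizes rather than power, and Table 3 is expressly for florbetapir. The Aim 1 point is a caution against carrying the conclusion over to tau.
- The 129 is approximate. BAI is not spelled out in the Précis (Banner Alzheimer's Institute is the natural reading), women who moved may attend another site, and imaging contraindications may reduce the count. None of these brings the number near 485.

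**Conclusion.** The concern holds. Section 9.4 claims 80% power at r = 0.127 without exception. For tau PET, planned in about 129 women, power at that correlation is about 30%, so a true correlation of that size would be missed about 70% of the time. The detectable r is about 0.245, roughly twice the stated value. Under Aim 1 the detectable d for tau is about 0.61, if the arms are equal.

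This rests on reading BAI as Banner Alzheimer's Institute, on the Table 1 projections, and on every woman enrolled at the two sites completing the scan. Incomplete scanning would lower power further, and full participation would raise it only to about 40%. The statements for Aβ, Table 3 and Objective 2 are not affected. It should be fixed, because the claim fails for a marker named in two primary hypotheses, though not for the designated primary outcome.

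**What to change.** - **Section 9.4, power:** restrict the 492 women, r = 0.127 and the closing sentence on small associations to markers measured at all sites. Add that AV-1451 is expected for about 129 women at two sites, subject to scan completion, with a detectable r of about 0.245 (R² about 0.06).
- **Section 9.2, power:** give the same N for tau and a detectable d of about 0.61 (equal arms assumed). Limit the remark on the remaining outcomes to those measured at all sites.
- **Analysis paragraphs for Aim 1 and Objective 3:** add AV-1451 SUVR, using the site adjustment already planned, applied to the two tau sites.
- **Optional:** label the tau contrasts exploratory.

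The cost is wording only. Data collection, sample size and the Aβ power statement do not change.

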9. DATA COLLECTION AND QUALITY ASSURANCE

10.1 Data Collection Forms

Case report forms (CRFs) have been developed in paper format and will also be made available as electronic CRF (eCRFs), or data entry screens, using infrastructure from the clinical trial management system Medidata Rave ™ Participant source data will be entered directly or transcribed into the eCRFs or captured on paper forms first and then transcribed into the

corresponding eCRFs. In particular, source data obtained at visit 1, including medical history, current use of medications, vital signs and questionnaires will be captured on paper forms and entered in eCRFs. MR images are stored in the Radiology clinical archiving system, and will be transferred to Mayo Clinic designated secure servers after anonymization. PET images are stored in Nuclear Medicine archiving system and will be transferred to Mayo Clinic designated secure servers after anonymization.

Paper CRF for cognitive and mood data will be stored at sites where data are collected. Study coordinators will enter coded data through a password protected, secure, web-based data portal (e.g., REDCap). All cognitive and mood data will be stored on a HIPAA-compliant, secure University of Wisconsin server. Keys linking identity of participants to coded data will remain at the data collection sites.

10.2 Data Management

Cognitive data will be transcribed into the Cognitive data portal, resulting in an eCRFs. The web-based system will be compliant with 21 CFR (Code of Federal Regulations) Part 11 FDA (Food and Drug Administration), Federal Information Security Management Act (FISMA), and Health Insurance Portability and Accountability Act (HIPAA) requirements. (e.g., REDCap) and will include features to guide data entry accuracy. For example, a reason range for data values will be designated, and an error message generated if values are out of range. Edit checks, electronic queries, and audit trails will be included to ensure accurate and complete data collection and security. https://www.project-redcap.org/

Cognitive data storage and management will occur under the direction of [name], with the assistance of a Master's-level statistician. Coded data will be stored in an R dataset with restricted access. As noted, the code will not be stored on the UW server, and will not be accessible to University of Wisconsin personnel.

Additional participant source data will be entered directly or transcribed into eCRFs using Medidata Rave ™, a remote system featuring advanced capabilities in both electronic data capture and clinical data management. Implemented via the Clinic Trials Management Systems (CTMS) project in 2010 the Medidata Rave ™system is compliant with 21 CFR (Code of Federal Regulations) Part 11 FDA (Food and Drug Administration) requirements. Edit checks, electronic queries, and audit trails are built into the system to ensure accurate and complete data collection and security.

Data storage and management at the Mayo Clinic is under the direction of [name], with the assistance of a Master's-level statistician. Data from Medidata Rave ™will be stored as SAS datasets (in Linux) with accessibility restricted to appropriate study members from the Division of Biomedical Statistics and Informatics in the Department of Health Sciences Research.

10.3 Quality Assurance

In addition to the quality assurance measures implemented at the data entry point, cognitive and mood data will be audited for outliers and inaccuracies through standard data cleaning procedures

Each MRI and PET acquired on a study subject scan is rated on image quality using a standardized grading form with electronic data entry into a database at the Mayo Clinic.

10.4 MRI Image Analysis

10.4.1 Pre-processing to Correct Specific Artifacts: Several common forms of image

- imperfection can degrade the quality of the MR data we will collect. These are intensity in-homogeneity due to B1 receiver non-uniformity; drifts or discontinuities in gradient calibration over time; and gradient non-linearity. Image pre-processing operations designed to correct these effects are applied to each set of images prior to image processing.
- 10.4.2 MRI analysis of regional cortical structure: 3D Magnetization Prepared Rapid Acquisition Gradient-Echo (MPRAGE) developed for the multi-center ADNI study by the Mayo ADNI team, 107 will be used to provide optimal tissue contrast for brain morphology and is harmonized across Siemens, GE and Phillips scanners. We will investigate the AD-signature region of interest (ROI) that we previously identified in clinically diagnosed and autopsy-confirmed AD patients and tested for diagnostic reliability and accuracy. 108 We will investigate both hippocampus and dorsolateral prefrontal cortex volumes because preservation of these structures have been observed after estadiol treatment in ovariectomized animal models. 109 Furthermore. the preliminary data in Figure 6 suggest that dorsolateral prefrontal cortex volume is preserved in the tE2 group compared to placebo seven years after starting mHT in the KEEPS MRI sub-sample. We will use both publically available FreeSurfer 5.3^{110,111} and in-house atlas-based ROIs for the analysis of regional volumes adjusted for total intracranial volume (TIV). In addition, we will conduct a non-hypothesis based voxel based morphometry (VBM) analysis using Statistical Parametric Mapping 12 (SPM12),112 to explore regional differences between the mHT and placebo groups in the entire brain using an unbiased approach.
- 10.4.3 Segmentation and Quantification of White Matter Hyperintensities (WMH) and identification of infarcts: Fluid attenuated inversion recovery (FLAIR) with TR/TE/TI = 6000/390/2100 ms with a 800 ms long turbo spin echo readout train, 750 Hz/pixel bandwidth with 3mm interleaved images of the whole head will be used. WMH volumes are measured using a semi-automated segmentation algorithm as previously described. 113 Briefly, FLAIR and MPRAGE images are co-registered, and the MPRAGE segmentation on SPM12 is used to create a WM mask to reduce false positives on the WMH segmentation from FLAIR. WMH is segmented using an automated slice-based seed initialization and region growing method. The segmented WMH voxels are multiplied with the WM mask and WMH masks are inspected and edited by a trained analyst (blinded to the treatment status) in order to exclude artifacts from the WMH volume. Infarcts will be identified by the same analyst and confirmed by [name]. The hyperintensities on FLAIR images associated with infarcts are marked and are re-classified as hyperintensities associated with cortical or subcortical infarcts. Hyperintensity associated with infarcts are not included in the WMH volume of individual subjects due to pathophysiologic differences between the two lesions. 114 We do not expect a significant number of infarcts in this cohort.
- 10.4.4 Diffusion Tensor Imaging (DTI): 2D single-shot gradient echo sequence with TR/TE=6600/86 ms, a 128 x 128 base matrix for 240 x 256 mm FOV, 60 contiguous 2 mm slices yielding 2.2 x 2.2 mm in-plane resolution is used for DTI. Diffusion-weighting gradients will be applied along 48 directions with b=1000 m²/s and 6 non-diffusion T2 volumes (b = 0 m²/s). This sequence was developed for the multi-center LEFFTDS and ARFL studies by the MCR team led by [name] and is harmonized across scanners in participating sites. We recently tested and validated a method to process DTI scans and analyze fractional anisotropy (FA) maps and demonstrated that improved DTI registration outperforms Tract-Based Spatial Statistics. 102 We will conduct non-hypothesis based voxel based analysis of FA to explore the WM diffusivity differences between each of the mHT and placebo groups in the entire white matter as previously described. 103
- **10.4.5** Resting state (Rs)-fMRI: A T2*-weighted gradient echo-echo planar sequence with TR/TE=2000/27 ms, flip angle 80°; FOV=230 x 230 mm; matrix size: 92 x 92; 3 mm

slices with 2.5 x 2.5 mm in-plane resolution will be used. Subjects are instructed to remain awake with their eyes closed. This sequence was developed for the multicenter LEFFTDS and ARFL studies by the MCR team led by [name] and is harmonized across scanners. The images will be realigned correcting for head motion, and unwarped correcting for susceptibility-by-movement interactions, slice-time corrected, co-registered to T1-weighted image, normalized and smoothed using SPM12. After processing, we will examine connectivity within the default mode network using a seed-based approach, by using the BOLD time series for specific regions as a covariate of interest for whole brain regression analyses. ^{105,106} Each of the mHT group maps will be compared to placebo groups with SPM12.

